3.3 Study population

Approximately 1500 MCI subjects will be screened in order to consecutively enrol 1000 participants according to the clinical criteria and assessments presented in table 2. All subjects will be enrolled according to the local mild cognitive symptom and clinical SOA procedures.

_

¹ the term "enrolled" refers to a participant's, agreement to participate in a clinical study following completion of the Informed Consent process and screening. Potential participants who are screened for the purpose of determining eligibility for the study, but do not participate in the study, are not considered enrolled, unless otherwise specified by the protocol.

Screening procedure

The screening procedure for inclusion in the Al-Mind study consists of two steps:

- Pre- (self-) screening: people who express their interest in participating in the AI-Mind study, will be given a screening questionnaire (in local language) targeting memory impairment. This test may be either self-administered (i.e. accessed electronically through an internet link), or administered by a clinician. In both cases the data will be collected through electronic forms (Nettskjema, see chapter 3.6). Only people who report mild symptoms, will be invited for further screening.
- Professional screening: Following, the potential participants will be given a local inclusion ID
 number and will proceed to the control of inclusion and exclusion criteria, as described
 below. If the subjects qualify for the study, they will be given the AI-Mind participant ID
 number.

Subjects fulfilling the Al-Mind criteria for MCI - based on the acknowledged criteria by the National Institute on Aging-Alzheimer's Association (NIA-AA) - and meeting the Al-Mind inclusion/exclusion criteria (listed below) will be offered participation in the Al-Mind clinical study. In principle, the clinical identification of MCI is defined by the participant's cognitive status. The assessment tools include Mini Mental Status Examination (MMSE), Montreal Cognitive Assessment (MoCA), Clinical Dementia Rating (CDR), Instrumental activities of daily living (IADL), and the Petersen/Winblad criteria (Petersen et al., 2004) (table 2).

Table 2: The criteria used for cognitive evaluation and later potential dementia progression

MCI Criteria	MCI Assessment	Dementia Progression Assessment	

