 Cognitive concern reported Objective evidence of impaired cognitive domain Persevered independence in functional abilities (ADCS-ADL >70%) Not demented (cognitive changes do not significantly impede social function or work activities) (Rule out vascular, other causes) Longitudinal decline (no lasting more than 3 years period at the enrolment time) Diagnostic and Statistical Manual of Mental Disorders, Fifth Edition, DSM – 5 	 CDR = 0.5 MMSE ≥ 25 Petersen/Winblad criteria, 1.5 SD in 1 or more domain Additional questionnaires: IADL/ADCS-ADL Montreal cognitive assessment (MoCa, ≥17) 	 CDR >0,5 MMSE ≤ 24 MoCa < 17 Petersen/Winblad criteria, 2 SD in 1 or more domain IADL below the limit of 70% 	

• Clinical Dementia Rating: The CDR® Dementia Staging Instrument uses a 5-point scale to characterise six domains of cognitive and functional performance applicable to dementia. The six domains are Memory, Orientation, Judgment & Problem Solving, Community Affairs, Home & Hobbies, and Personal Care. The rating is done by a semi-structured interview of the tested subject and a reliable informant or collateral source (e.g. a family member) referred to as the CDR® Assessment Protocol. Using the CDR® Scoring Table a subject's level of impairment/dementia is characterized: 0 = Normal, 0.5 = Very Mild Dementia, 1 = Mild Dementia, 2 = Moderate Dementia, 3 = Severe Dementia.

- Deliverable No. **D5.1** Version 1
- Mini Mental State Examination (MMSE): The MMSE is a brief, quantitative measure of cognitive status. It can be used to screen cognitive impairment, to estimate the severity of cognitive impairment at a given point in time, to follow the course of cognitive changes in an individual over time, and to document an individual response to treatment. Measurements of cognitive function include registration (repeating named prompts), attention and calculation, recall, language, ability to follow simple commands and orientation. Score of 24 or more (out of 30) is considered a normal cognition. Below this, scores can indicate severe (≤9 points), moderate (10−18 points) or mild (19−23 points) cognitive impairment.

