- Montreal Cognitive Assessment (MoCa): Due to ceiling effects in light MCI cases by the MMSE, the MoCa test will be used as well in assessing people affected by MCI. MoCa is a 30-question test that takes around 10 to 12 minutes to complete. MoCA evaluates cognitive abilities including Orientation, Short term memory/Delayed Recall, Executive Function/Visuospatial Ability, Language Abilities, Abstraction, Animal Naming, Attention and Clock-Drawing Test. Because it tests the executive function, it is considered more sensitive in this regard compared to MMSE.

In addition, the following inclusion and exclusion criteria must be fulfilled to enrol subjects in the study:

Inclusion criteria

- Male and female aged between 60 and 75 years.
- Al-Mind MCI assessment listed in table 2.
- Capable of giving signed Informed Consent, which includes compliance with the requirements and restrictions listed in the Informed Consent and in this protocol.

Exclusion criteria

- AI-Mind dementia criteria listed in table 2.
- History of cerebrovascular disease (i.e., major stroke episodes).
- Alcohol Dependence Scale AUDIT score positive.
- Severe medical disorders associated with cognitive impairment (organ insufficiencies, chronic infections, endocrine disorders) which produce chronic uncompensated failure.
- Severe head trauma with structural brain lesion and/or previous brain surgery.
- Severe mental disorders; Schizophrenia, known Major depression or bipolar disorder.
- Neuroimaging evidence of other potential causes of cognitive decline (e.g. subdural hematoma, brain malignancy, metabolic encephalopathy).
- History of non-brain malignancy < 5 years.
- Recent use of psychotropic drugs including AChEI and Memantine < 3 months.
- Participation in trials with experimental drugs.

The age specification is set between the age of 60 - 75 years at enrolment to avoid increasing confounding factors by age, causing cognitive function loss.

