There is a documented dementia uneven prevalence of 2:1 in MCI, affecting females more often than males (The Economist Intelligence Unit Limited, 2017). This epidemiological aspect will be addressed during the AI-Mind AI-tool developments and validation to ensure that relevant gender-associated biomarkers are not omitted. Due to this gender discrepancy, it can be hypothesised that there will be an increased prevalence of female-derived available and prospective data for inclusion, which could result in bias during tool development. Using state of art techniques to mitigate the bias of the AI algorithms development will ensure that the collected data is representative for both genders even though the data might be unbalanced due to the prevalence in female subjects.

Furthermore, unanimously at the General Assembly meeting on the 17th of September 2021, all sites decided to integrate supplemental SOA neuropsychological assessments to pre-screen potential

participants. These evaluations will be administered at each site during recruitment screening, covering different cognitive areas: memory, attention, executive functions, visuospatial skills and language. The scores obtained in these additional neuropsychological assessments will be included in Case Report Forms (CRF, table 3 and Annex I).

Table 3: Schedule of Activities

Procedure	Recruitment screening		Follow-up (weeks/months)			Notes
		то	T1	T2	Т3	
		0	8	16	24	
Informed consent signed	Х					
Inclusion and exclusion criteria	Х					
Sociodemographic and Anamnestic Data	Х					
Clinical history	Х					
Somatic and neurological physical examination	Х	Х	Х	Х	Х	
FFQ (Food frequency questionnaire)		Х				
Risk Factors	Х	Х				
Assessment of Somatic Comorbidity	Х	Х				
Current Therapy	Х	Х	Х	Х	Χ	
Memory Questionnaire	Х	Х			Χ	
AI-Mind MCI criteria, table 3	Х					
RAVLT (Rey Auditory Verbal Learning test)		X			Х	
ROCF (Rey-Osterrieth complex figure test)		Х			х	
Boston Naming Test		Х			Х	
Category Fluency		Х			Х	
TMT (A,B,B-A)		Х			Х	
Letter fluency		Х			Х	
128 lead EEG		Х	Х	Х	Х	
CANTAB – digitalised cognitive assessment		Х	Х	Х	Х	
MEG		Х			Х	only at UCM and HUH
Blood sample collection		Х				APOE, P-tau variance

Subgroup for MEG procedure

At UCM and HUH, a minimum of 70 patients per site will be measured with simultaneous M/EEG recordings. The localisation accuracy of MEG will be used for extracting the most relevant features for EEG data analysis.

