Annex I

CRF – Nettskjema

Al-Mind: Case Report Form for Inclusion

Page 1 Mandatory fields are marked with a star * Clinician's name and contact information The name of the project associate filling in the CRF form (first name and surname)? * Not the participant's name. What is your e-mail address? * Not the participant's email. Page break Page 2 Mandatory fields are marked with a star * **Local Inclusion ID** The *Inclusion ID* is a code used for local management of potential participants *prior* to inclusion into the Al-Mind study. Once the participant is included in the study, they will receive their Participant ID. Don't know the participant's Inclusion ID? Please contact the clinical site Pl. Page break Page 3 Mandatory fields are marked with a star *

INCLUSION CRITERIA CHECKLIST

Age be	etween 60 and 75 years (at the time of inclusion)?
0	Yes
0	No
Cognit	ive concern reported by participant and/or a proxy caregiver? *
0	Yes
0	No
Object abilitie	ive evidence of impaired cognitive domain (yet preserved independence in functional s)? *
0	Yes
0	No
Not de	emented; cognitive changes do not significantly impede social function or work activi-
0	Yes
0	No
Longit	udinal decline (not lasting more than 3 years period at the enrollment time) *
0	Yes
0	No
DSM-	5 diagnosis "MCI" at the time of inclusion? *
0	Yes
0	No

Are vascular (stroke) or other causes of the cognitive impairment ruled out? *

	ŕ
O Yes	
O No	
MMSE ≥ 25 or MoCA ≥ 17? *	
O Yes	
O No	
(I)ADL/ADCS-ADL > 70%? *	
O Yes	
O No	
Petersen/Winblad criteria, 1.5 SD in 1 or more domain fulfilled	d? *
O Yes	
O No	
CDR ≤ 0.5? *	
O Yes	
O No	
Page break	
	Page 4

Mandatory fields are marked with a star *

EXCLUSION CRITERIA CHECKLIST

0	
	Yes
0	No
Alcoho	ol Dependence Scale (e.g. AUDIT) score positive? *
0	Yes
0	No
_	evere medical disorders associated with cognitive impairment (organ insufficiencies, c infections, endocrinical disorders) which produce chronic uncompensated insuffi- ? *
0	Yes
0	No
Any se	evere head trauma with structural brain lesion and/or previous brain surgery? * Yes
0	No
-	evere mental disorders (e.g. schizophrenia, known major depression or bipolar disor-
-	evere mental disorders (e.g. schizophrenia, known major depression or bipolar disor-
-	evere mental disorders (e.g. schizophrenia, known major depression or bipolar disor-
der)?	evere mental disorders (e.g. schizophrenia, known major depression or bipolar disor-

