der)?	evere mental disorders (e.g. schizophrenia, known major depression or bipolar disor- Yes No euroimaging evidence of other potential causes of the cognitive decline (e.g. subdural

History of malignancy < 5 years? *	
O Yes	
O No	
Recent use of psychotropic drugs including AChEI and Memantine (< 3 months)? *	
O Yes	
O No	
MMSE ≤ 24 or MoCa < 17? *	
O Yes	
O No	
Petersen/Winblad criteria, 2 SD in 2/3 cognitive domain/according to MCI criteria *	
O Yes	
O No	
Positiv (I)ADL score (retained function) less than 70%? *	
O Yes	
O No	
Page break	
	Page 5

Mandatory fields are marked with a star *

ASSESSMENT SCALE RESULTS

Cognitive functioning

Cognitive fu	nctioning scale *
Specify which	n scale has been used to assess cognitive functioning .
O MMSE	
O MoCA	
Other (s	specify below)
Specify which	ch assessment scale was used to assess cognitive functioning *
	ment is only shown when the option "Other (specify below)" is selected in stion "Cognitive functioning scale"
Cognitive fu	nctioning scale score *
Ü	the score obtained with the assessment scale.
Activities	of Daily Living (ADL)
ADL scale *	
Specify which	h of the ADL scales has been used.
O IADL	
O ADL-MO	
Other (s	specify below)
Specify which	ch of ADL scales was used *
	ment is only shown when the option "Other (specify below)" is selected in stion "ADL scale"
ADL scale s	score *
Please enter	the obtained positive ADL score (i.e., the percentage of intact function).

Clinical Dementia Rating (CDR)

Use the calculator found here to compute the Global Score.

CDR scale G	Blobal Score *
Please enter t	he obtained CDR-Global Score.
Depressio	n
Depression s	cale *
Specify which	scale has been used to assess depression .
O MADRS	
O GDS	
Other (sp	pecify below)
Specify whicl	h assessment scale was used to assess depression *
This elem	nent is only shown when the option "Other (specify below)" is selected in ion "Depression scale"
Depression s	he score obtained with the assessment scale.
riodoo ontor a	To doore obtained with the doodselfield doubt.
Alcohol ak	ouse
Link to online	AUDIT screening.
Alcohol abus	e scale *
Specify which	scale has been used to assess alcohol abuse .
O AUDIT	
Other (sp	pecify below)
Specify whicl	h assessment scale was used to assess alcohol abuse *
	nent is only shown when the option "Other (specify below)" is selected in ion "Alcohol abuse scale"

Alcohol abuse scale score *	
Please enter the score obtained with the assessment scale.	
E Page break	
	Page

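### The 2 SD dementia cut needs at least one domain in Table 2 but at least two on the CRF exclusion checklist, so a person can pass the form while already meeting an exclusion and progression item

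*Protocol*

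**What the plan says.** Table 2 in section 3.3 of the protocol is captioned "The criteria used for cognitive evaluation and later potential dementia progression", so one table serves both entry and outcome. Its MCI column requires "Petersen/Winblad criteria, 1.5 SD in 1 or more domain". Its dementia progression column lists "Petersen/Winblad criteria, 2 SD in 1 or more domain" beside cut-offs on CDR, MMSE, MoCA and IADL, without saying whether one item is enough or several are needed. The first exclusion criterion in section 3.3 is meeting the "dementia criteria listed in table 2".

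The inclusion form in Annex I repeats the entry item unchanged: "Petersen/Winblad criteria, 1.5 SD in 1 or more domain fulfilled". Its exclusion checklist, a mandatory yes/no field, words the dementia cut differently: "Petersen/Winblad criteria, 2 SD in 2/3 cognitive domain/according to MCI criteria". The form defines neither the 2/3 nor the closing reference to MCI criteria.

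**The concern.** Two eligibility thresholds for the same construct stand in one document and disagree about an identifiable group: people with one domain, and only one, at or below -2 SD. The entry item has no lower limit, so these people satisfy it. No other item on the form tests the 2 SD domain cut. The MMSE/MoCA, ADL, CDR and not-demented items may remove some of them, but only incidentally.

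The eligibility threshold is also an outcome threshold. The primary endpoints in Table 1 include the Predictor's 24-month prediction and its sensitivity and specificity above 0.9. If the 2 SD item alone can make someone a progressor, a participant who met it at entry can be called progressed although nothing has changed. Part of the measured performance would then be recognition of baseline status. The section 5 rule that participants who develop exclusion criteria leave the study would also bite at different points under the two wordings.

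**Working it through.** **Comparing the rules.** Let k be the number of domains at or below -2 SD in a person who meets the 1.5 SD entry item.

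| k | Table 2 with the section 3.3 exclusion | Annex I exclusion item |
|---|---|---|
| 0 | not excluded | not excluded |
| 1 | excluded; progression item met | not excluded |
| 2 or more | excluded | excluded, if 2/3 means two or three domains |

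If 2/3 means two out of three particular domains, or all of three, the form excludes fewer still. The rules differ at k = 1 on each of these readings.

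**How large the k = 1 group might be.** The protocol gives no figure to reproduce, so what follows is an illustration on assumptions.

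- Domains: five, from section 3.3, which describes the screening tests as "covering different cognitive areas: memory, attention, executive functions, visuospatial skills and language".
- Assumed: normal domain z-scores with a common correlation of 0.3-0.5 and a mean of 0 to -1.0.
- Entry: lowest z at or below -1.5. Passing the form: entry and k of 0 or 1.
- Quantity: P(k = 1 | entry, k ≤ 1) = P(k = 1 | entry) / [1 - P(k ≥ 2 | entry)].

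One setting in full: with mean -0.5 and correlation 0.4, 34.9% of those meeting the entry item have k = 1 and 16.3% have k ≥ 2. The share is 0.349 / (1 - 0.163) = 0.349 / 0.837, or about 42%.

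| Assumptions | Share with k = 1 among those passing the form's SD items |
|---|---|
| Five domains, SD items only | 33-53% |
| Same, plus a stand-in for the other mildness criteria (mean z above -1) | 20-33% |
| 3 or 5 domains, mean -0.5 to -1.5, correlation 0.2-0.6, SD items only | 37-65% |

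**What is due to the discrepancy.** Suppose nobody truly changes and retest reliability is 0.7-0.9. Without the mildness filter, 26-52% of those admitted by the form meet the one-domain 2 SD item at month 24. Under the Table 2 exclusion the figure is still 18-38%, because scores just above a cut cross it by retest error. Only the difference between the two rules, taken within each setting, belongs to this inconsistency. With the mildness filter and reliability 0.8 it is roughly 4-8 percentage points (as low as 3 if errors are independent between domains). It is larger at higher reliability or without the filter.

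**The case against.** The strongest reply is that the section 3.3 text governs. Professional screening is described there as a check of the criteria listed in that section, and section 3.6 describes the CRF as a means of collecting information. On that view such a person is excluded whatever the form says. The closing words of the form's item might also be meant to point back to the protocol criteria. This limits the point: the documents support saying that these people can be enrolled where the form's wording is applied, not that they are enrolled. It does not remove the inconsistency, because staff completing the form answer a question with a different threshold.

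Four stronger readings may tempt a reader.

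- *Such a person counts as progressed on day 0.* Table 2 does not say whether its items combine by any or by all, and section 5 leaves analysis detail to the statistical analysis plan. The form's separate yes/no items favour any for exclusion, but nothing fixes the 24-month label. If all items are needed, one domain at -2 SD is not progression and, strictly, not an exclusion either.
- *Sites will enrol different populations.* Annex I shows one form, and no site difference on this item is documented.
- *The one-domain rule cannot give 1000 from 1500.* The protocol says "Approximately 1500 MCI subjects will be screened in order to consecutively enrol 1000 participants". With the SD items alone, the Table 2 rule keeps 0.338-0.609 of those meeting the entry item, and 1500 × 0.338 = 507 to 1500 × 0.609 = 914. With the mildness filter it keeps 0.66-0.80, and 1500 × 0.66 = 990 to 1500 × 0.80 = 1200. The shortfall comes from the modelling choice, so this argument fails.
- *The whole month-24 positive rate is an artefact of the form.* Most of it would also occur under Table 2.

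It is also fair to say that the individual test scores are recorded and the battery is scheduled at T0 and T3, so baseline status can be derived given norms. That makes the problem repairable, but only if the repair is planned.

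**Conclusion.** The inconsistency is certain and rests on the text alone: the same dementia cut takes one domain in Table 2 and at least two on the form, and people with exactly one domain at or below -2 SD fall between them. They can pass the form while meeting a Table 2 exclusion and progression item.

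The bias in sensitivity and specificity is conditional on the Table 2 items being used singly for the 24-month label. The 20-53% range shows that the group need not be small, but it depends on assumed correlations and means, and chiefly on how strongly the MMSE, MoCA, CDR and ADL criteria remove severe cases. It is not an estimate for this cohort. The protocol's screening figure is not called into question.

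**What to change.** 1. Reconcile Table 2, the section 3.3 exclusion and the Annex I item to one stated number of domains, replacing 2/3 and the undefined reference to MCI criteria. Which number is for the investigators to decide.
2. Count the 2 SD item towards progression only if it was not already met on the baseline neuropsychological scores. State beside it whether the Table 2 items combine by any or by all.
3. Check any participant entered under the form's present wording for exactly one domain at or below -2 SD, and document how they are handled.

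The cost is one edit to the form, one line in Table 2 or section 3.3, one sentence in the outcome definition and, if enrolment has begun, a data query. No new assessments are needed, though deriving domain status requires the national norms and a stated allocation of tests to domains. The count of progressors may fall. The work is cheapest before enrolment, since each entry under the wrong wording adds a case to resolve.

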1.2 Outcomes

The main outcomes regarding the Clinical Study Dossier and clinical study procedures are summarised below.

Inclusion and exclusion criteria

The definition of inclusion and exclusion criteria is based on an extensive literature review and the internal Al-Mind partners` agreement to adhere to the project's objectives.

Definition of MCI at enrolment

General consensus of the criteria to define MCI for the clinical study participants. The inclusion criteria define the degree of cognitive impairment and a minimum of test assessments (table 2).

Ethical requirements and Informed Consent before enrolment

All clinical sites followed the local ethical procedures in alignment with relevant national and EU laws and regulations. An independent Al-Mind ethics advisor has been appointed. Feedback from the user representing association Alzheimer Europe has been implemented.

Ethical Committee approvals

The study has been approved by the Ethical Committees of all clinical sites in due course. The final consensus of the used clinical guidelines, procedures and formation have been incorporated into the application. All Informed Consents have been approved.

Definition of demographic and clinical data collection

Various clinical variables (e.g. demographics, weight, etc.), information about well documented associated pathologies and interventions will be collected. These data will be analysed in order to determine their influence on the risk of progression to dementia for population with MCI.

Blood sample collection, storage and shipment

Blood samples will be collected at the first visit, to determine their APOE allele constellation and individual P-Tau associated P181 and/or P217 protein levels. The samples will be collected, stored and shipped according to standardised procedures (Deliverable 2.1).

Harmonisation of EEG recording and storage

All technological aspects for the EEG recording have been standardised and agreed on among the experts from the five clinical sites. All sites will use identical 128-channel EEG devices and harmonised recording parameters (amplification, sampling rate, filters, artefact recognition, duration of each session etc). The characteristics of the recording environment (baseline noise/light brightness) have been standardised (Deliverable 2.1).

Digitalised Cognitive Testing (CANTAB)

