Mandatory fields are marked with a star *	
NEUROPSYCHOLOGICAL TEST SCORES	
Rey Auditory Verbal Learning Test (RAVLT)	
RAVLT: Learning, trial 1	
RAVLT: Learning, trial 2	
RAVLT: Learning, trial 3	
RAVLT: Learning, trial 4	
DAVII To Learning trial 5	
RAVLT: Learning, trial 5	
RAVLT: Delayed recall	
RAVLT: Recognition	
TVAVET. TVeGOGITILIOTI	
RAVLT: Recognition, false positives	

Al-Mind: Case Report Form for Inclusion - View - Nettskjema **Rey-Osterrieth Complex Figure Test (ROCF)** ROCF: Time used ROCF: Copy **ROCF: Delayed recall ROCF**: Recognition **Boston Naming Test (BNT) BNT: Score Category Fluency (CF)** CF: Total score **CF: Total errors Trailmaking Test (TMT)** TMT: A In seconds.

TMT: A, number of errors

TMT: B	
In seconds.	
TMT: B, number of errors	
Letter Fluency (LF)	
LF: Letter 1	
LF: Letter 2	
LF: Letter 3	
LF: Total errors	
Page break	
	Page 7
Mandatory fields are marked with a star *	
CLINICAL HISTORY	
Months since onset of cognitive symptoms *	
Please round up or down to nearest whole month.	

Type of symptoms debut *	
☐ Acute	
Subacute	
Insidious	
Unknown	

Checklist of cognitive symptoms
Memory (amnesia)
No
O Yes
Unknown
Language (anomia, speech trouble)
No
O Yes
OUnknown
Motor programming (apraxia)
No
Yes
O Unknown
Recognition of objects/faces (agnosia/prosopagnosia)
No
O Yes
OUnknown
Attention
No
O Yes

0	Unknown
Planni	ng (executive function disorder)
•	No
0	Yes

Unknown

Checklist of other symptoms
Extrapyramidal
No
Yes
OUnknown
Focal motor
No
O Yes
Unknown
Falls
No
O Yes
OUnknown
Fluctuations
No
O Yes
OUnknown
Sleep disorders
No
O Ves

Al-Mind: Case Report Form for Inclusion - View - Nettskjema Checklist of psychiatric symptoms/behavioural abnormalities Anxiety • No Yes Unknown Depression • No Yes Unknown **Apathy** • No Yes Unknown Lack of concern **①** No

Fatuity

0	Unknown
Disinh	ibition
•	No
0	Yes
0	Unknown
Aggres	ssiveness
•	No
0	Yes
0	Unknown
Fixed	ideas/delusion
•	No
0	Yes
0	Unknown
Halluc	inations
•	No
0	Yes
0	Unknown
Poor s	elf-care/grooming
•	No

0	Yes
0	Unknown
Lack c	of awareness
•	No
0	Yes
0	Unknown
Page	break
1=1 -	
	Page 8
Mandato	Page 8 ory fields are marked with a star *
SOM . Height	ATIC AND NEUROLOGICAL PHYSICAL ASSESSMENT *
SOM . Height	ory fields are marked with a star * ATIC AND NEUROLOGICAL PHYSICAL ASSESSMENT
SOM . Height	ATIC AND NEUROLOGICAL PHYSICAL ASSESSMENT *
SOM . Height	ATIC AND NEUROLOGICAL PHYSICAL ASSESSMENT * round up or down to nearest whole cm.

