SOM. Height Please Weigh	ATIC AND NEUROLOGICAL PHYSICAL ASSESSMENT * round up or down to nearest whole cm.
SOM. Height Please Weigh	ATIC AND NEUROLOGICAL PHYSICAL ASSESSMENT t * round up or down to nearest whole cm. t *
SOM. Height Please Weigh Please	ATIC AND NEUROLOGICAL PHYSICAL ASSESSMENT t * round up or down to nearest whole cm. t *
SOM. Height Please Weigh Please Abdon	ATIC AND NEUROLOGICAL PHYSICAL ASSESSMENT t * round up or down to nearest whole cm. t * round up or down to nearest whole kg.
SOM. Height Please Weigh Please Abdon	ATIC AND NEUROLOGICAL PHYSICAL ASSESSMENT t * round up or down to nearest whole cm. t * round up or down to nearest whole kg.
SOM. Height Please Weigh Please Abdon Please	ATIC AND NEUROLOGICAL PHYSICAL ASSESSMENT t * round up or down to nearest whole cm. t * round up or down to nearest whole kg.
SOM. Height Please Weigh Please Abdon Please	ATIC AND NEUROLOGICAL PHYSICAL ASSESSMENT t * round up or down to nearest whole cm. t * round up or down to nearest whole kg.
SOM. Height Please Weigh Please Abdon Please Blood	ATIC AND NEUROLOGICAL PHYSICAL ASSESSMENT t * round up or down to nearest whole cm. t * round up or down to nearest whole kg. ninal circumference * round up or down to nearest whole cm. pressure (systolic)

Blood pressure (diastolic) In mmHg .
Total cholesterol
f available, please provide a recent value (max. 1 year).
Neurological signs *
Other than cognitive symptoms.
O No
O Yes
Please specify the neurological signs
This element is only shown when the option "Yes" is selected in the question "Neurological signs"
Use keywords.
Sleep disorders
O No
O Yes
O Don't know
Burnout or severe stress over time
s it highly probable that the person's cognitive symptoms are caused by burnout or severe stress over time?
O No
O Yes
O Don't know
Page break

Page 9

Mandatory fields are marked with a star *

RISK FACTORS
Dementia
Total number of first-degree relatives with dementia
Include all first-degree relatives with a known dementia condition, both deceased and alive.
Relatives with dementia?
O No
O Yes
O Don't know
Specify the relative who has/had dementia
This element is only shown when the option "Yes" is selected in the question "Relatives with dementia?"
Multiple answers may be selected.
☐ Mother
☐ Father
☐ Sister(s)
☐ Brother(s)
How many sisters are/were affected by dementia?
This element is only shown when the option "Sister(s)" is selected in the question "Specify the relative who has/had dementia"

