•	This element is only shown when the option "Don't know (describe)" is selected in the question "Is the patient's hypertension severe?"
Vasc	cular pathologies (blood, vessels, marrow, spleen, lymphatic system) *

No

O Yes

Is the patient's vascular pathology severe? *

•	This element is only shown when the option "Yes" is selected in the question "Vascular pathologies (blood, vessels, marrow, spleen, lymphatic system)"			
0	No			
0	Yes			
0	Don't know (describe)			
Describe the patient's vascular pathology				
•	This element is only shown when the option "Don't know (describe)" is selected in the question "Is the patient's vascular pathology severe?"			
Resp	piratory diseases (lungs, bronchi, trachea under the larynx) *			
•	No			
0	Yes			
Is the patient's respiratory disease severe? *				
•	This element is only shown when the option "Yes" is selected in the question "Respiratory diseases (lungs, bronchi, trachea under the larynx)"			
0	No			
0	Yes			
0	Don't know (describe)			
Describe the patient's respiratory disease				
•	This element is only shown when the option "Don't know (describe)" is selected in the question "Is the patient's respiratory disease severe?"			
O.O.N.G.L. (eye, ear, nose, throat, larynx) *				
•	No			
0	Yes			

Deliverable No. **D5.1** Version 1

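### On the CRF symptom checklists and top-level comorbidity items *No* appears preselected, so an untouched item cannot be told from a true *No* and can misclassify covariates

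*Protocol*

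**What the plan says.** Annex I prints the electronic inclusion form. On its page 7 (clinical history) there are 22 symptom items in three checklists, each offering *No*, *Yes* and *Unknown*. In the psychiatric block the text reads "Anxiety • No Yes Unknown Depression • No Yes Unknown", and a neighbouring item reads "Lack of concern ① No". None of the 22 items is starred. The form's rule is "Mandatory fields are marked with a star", so these items may be left untouched.

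On page 10 (chronic somatic comorbidity) the top-level items are starred and offer only *No* and *Yes*. Hypertension, "Respiratory diseases (lungs, bronchi, trachea under the larynx") and "O.O.N.G.L. (eye, ear, nose, throat, larynx") show the same distinct mark before *No*. A starred severity question opens only when *Yes* is chosen.

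Section 1.2 says of clinical variables, including associated pathologies: "These data will be analysed in order to determine their influence on the risk of progression to dementia for population with MCI". Section 3.2 lists medical history among the background parameters to be investigated as possible confounders.

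**The concern.** If *No* is preselected, the stored value has two meanings: the clinician judged the feature absent, or nobody answered. On the symptom items this defeats the purpose of the *Unknown* option. On the comorbidity items the mandatory check cannot reveal an omission, because the default already satisfies it, and the severity question never appears. A condition that is present but left untouched enters the database as absent. At stake is the accuracy of symptom and comorbidity covariates. A later analysis plan could not tell from these fields alone which *No* entries were real answers.

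**Working it through.** **Step 1. Is there a default?** The protocol does not state one, so the option marks have to be compared.

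| Part of the form | Mark before *No* | Mark before the other options |
|---|---|---|
| Page 7, symptom items | filled mark on 10 of 22 items; a different non-empty mark on an eleventh; no mark on the rest; the open marker on none | open marker or none |
| Page 10, hypertension, respiratory, O.O.N.G.L. | filled mark | open marker |
| Page 10, severity sub-questions | open marker | open marker |
| Page 8, neurological signs and sleep disorders; page 9, "relatives with dementia" | open marker | open marker |

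Ten of the eleven marked symptom items are in the psychiatric block, which has eleven items; the other is the planning item. The comparison within page 10 is the most telling: the same page gives two different marks for *No*, so the filled mark is not simply how *No* was read from the PDF. A preselected *No* on the marked items is the best explanation.

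**Step 2. What would it do?** The protocol gives no item skip rate, prevalence or odds ratio for these covariates, and has no figure of its own to reproduce. Everything below is an assumption for illustration.

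Let p be the true prevalence and s the share of items left untouched, independently of the true value. A true *Yes* is then recorded with probability 1 − s, and a true *No* is always recorded correctly:

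- recorded prevalence q = p(1 − s)
- recorded OR = [q1/(1 − q1)] / [q0/(1 − q0)], with 1 = progressors and 0 = non-progressors

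Example with p1 = 0.40, p0 = 0.25, s = 0.10: q1 = 0.36 and q0 = 0.225; the odds are 0.36/0.64 = 0.5625 and 0.225/0.775 = 0.2903; OR = 0.5625/0.2903 = 1.94.

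| True prevalence, progressors / non-progressors | True OR | s = 10% | s = 20% | s = 30% |
|---|---|---|---|---|
| 40% / 25% | 2.00 | 1.94 | 1.88 | 1.83 |
| 80% / 60% | 2.67 | 2.19 | 1.93 | 1.76 |

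Equal skipping pulls the odds ratio towards 1, modestly for less common features and more for very common ones. A true OR of 1.0 stays at 1.0, and with no skipping nothing changes.

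**Step 3. Unequal skipping.** Take 20% skipped in one outcome group and 5% in the other, with a true OR of 1.0. At 50% prevalence, q1 = 0.50 × 0.95 = 0.475 and q0 = 0.50 × 0.80 = 0.40, so OR = (0.475/0.525)/(0.40/0.60) = 1.36. With the groups reversed it is 0.74. The corresponding ranges are 0.79 to 1.26 at 30% prevalence and 0.83 to 1.21 at 10%. With a true OR of 2.0 and 30% prevalence in non-progressors, the recorded value lies between 1.47 and 2.47. This form is completed at inclusion, before the outcome is known, so such a difference would have to arise indirectly, for example through site.

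**The case against.** The strongest reply is that the evidence is a typographical mark in text read from a PDF, and an uneven one. Five of the six cognitive items and all five items under other symptoms show no mark on *No*. Of the five comorbidity items that can be read, heart disease and vascular pathologies show none. The same filled mark also stands for the icon before conditional-display notes, and blanks fall on other options as well. This stands against a reader who infers that the default is shown for every item. It does not explain the contrast within page 10 or the run of marked items in the psychiatric block.

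A second reply is that the data are entered by delegated site staff (section 3.6), who may answer every item. That stands: without skipping there is no error, so it would be wrong to say that the default biases the analyses as such.

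Third, a reader might infer that errors could never be found. The documents do not support that. Depression also has a starred scale and score on page 5 of the form. Sleep disorders are asked again on page 8 without a default. Table 3 schedules somatic comorbidity at both screening and T0, and current therapy at every visit. These checks are partial: Table 3 schedules clinical history at screening only, so most symptom items have no direct repeat.

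Fourth, section 1.2 names associated pathologies, not symptom checklists, and the page headed risk factors shows no preselected answer. The link to planned analyses is therefore firmer for comorbidity and medical history than for symptoms, and does not extend to family history, smoking, substance use or physical activity.

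**Conclusion.** A small, conditional point holds. On the marked symptom and top-level comorbidity items *No* appears preselected, and if the live form confirms this, an untouched item is indistinguishable from a true *No*. That can misclassify covariates, including associated pathologies and medical history that the protocol intends to analyse. With equal skipping of 10% to 30%, the illustrative OR of 2.00 falls to between 1.94 and 1.83; for a very common feature the loss is larger. With skipping that differs by outcome or site, the direction is not predictable and a false association is possible. All of this rests on assumed skip rates and prevalences.

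A reader might infer that the primary results are at risk. The documents do not show that: the enrichment inputs that section 3.1 names for the Predictor, beyond the EEG-based Connector, are digital cognitive tests, APOE and p-Tau, and nothing ties the sensitivity and specificity endpoints to these CRF items.

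**What to change.** Confirm the setting on the live form. If *No* is preselected:

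- remove the default from the symptom and top-level comorbidity items;
- make the symptom items mandatory with *No*, *Yes* and *Unknown*;
- add *Unknown* to the top-level comorbidity items.

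For records already entered, check *No* entries against the T0 comorbidity assessment, current therapy, the depression scale and the second sleep item, and flag the rest as possibly misclassified. First make sure that the T0 comorbidity assessment was not entered on a form with the same default, or it is no independent check.

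The cost is a form setting, a few more clicks per participant, and some values recorded as unknown. Early action limits the number of ambiguous records.
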